# 6.16.1.4. COVID-19-Related Deterioration (COVID-19-Related Hospitalization, or Death from Any Cause)

The proportion (percentage) of participants who experience COVID-19 related deterioration, defined as experiencing either of the following events by Day 22, 29, 60 and 85 will be analyzed:

- COVID-19-related hospitalization (defined as ≥24 hours of acute care), or
- death from any cause

In addition, the proportion (percentage) of participants who experience any of the following events by Day 29 will be analyzed:

- COVID-19 related emergency room visit, or
- COVID-19-related hospitalization (defined as ≥24 hours of acute care), or
- death from any cause

The efficacy population will be utilized to analyze COVID-19-related deterioration.

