2.10.3. Section 9.3. Populations for Analyses

This table defines the pediatric populations for analysis.

Pediatric Population for Analysis	Description
Pharmacokinetic	All pediatric participants who received a full dose of study intervention and have at least one evaluable PK sample.
Safety	All pediatric participants who received study intervention.
Efficacy	All pediatric participants who received study intervention and provided at least one post-baseline measure for the relevant endpoint.

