# 6.1.1. Analysis Populations

Patient populations are defined in Table PYAB.6.1 along with the analysis to be used to conduct. The treatment groups and inferential comparisons described in Table PYAB.6.1 will be used unless otherwise specified.

Table PYAB.6.1. Analysis Populations

Population	Description	
Entered	Definition: All participants who signed informed consent/assent.	
	Purpose: Used for disposition analysis.	
	Treatment Groups: None	
	Inferential Comparisons: None	
Per-Protocol	Definition: All participants in the efficacy population who do not meet any of the following criteria:	
	did not meet an inclusion criterion; or	
	met an exclusion criterion.	
	Purpose: Used for sensitivity analyses for the primary and key secondary endpoints.	
	Treatment Groups (Short Label):	
	Bebtelovimab weight-based dosing.	
	Inferential Comparisons:	
	None, as this is a single-arm cohort.	
Efficacy	Definition: All enrolled participants who received study intervention and provided at least 1 postbaseline efficacy measurement.	
	Purpose: Used for efficacy variable analyses.	
	Treatment Groups (Short Label):	
	Bebtelovimab weight-based dosing.	
	Inferential Comparisons:	
	None, as this is a single-arm cohort	
Safety	Definition: All enrolled participants who received any amount of study intervention.	
	Purpose: Used for safety analyses, analyses of COVID-19-related deterioration and hospitalization events.	
	Treatment Groups (Short Label):	
	Bebtelovimab weight-based dosing.	
	Inferential Comparisons:	
	None, as this is a single-arm cohort.	
Pharmacokinetic and PK/PD	Definition: All enrolled participants who received study intervention and have	
(exposure-response	at least 1 post dose PK sample.	
relationships)	Purpose: Used for PK analyses.	
	Treatment Groups (Short Label):	
	Bebtelovimab weight-based dosing.	
	Inferential Comparisons:	
	None, as this is a single-arm cohort.	

Abbreviations: COVID-19 = coronavirus disease 2019; PD = pharmacodynamic; PK = pharmacokinetic; SC = subcutaneous.

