### 6.16.1.2. Symptom Resolution

Participants will be assessed for the presence of symptoms associated with COVID-19 by a daily questionnaire. This questionnaire is for outpatient participants only.

The questionnaire contains these symptoms:

shortness of breath or difficulty breathing congestion or runny nose fever chills sore throat stomachache nausea vomiting diarrhea cough tiredness muscle or body aches and pains headache loss of taste loss of smell poor appetite or poor feeding

The presence or absence of symptoms associated with COVID-19 within the past 24 hours will be collected from participants or their parents/legal guardian.

Symptom resolution is defined as all symptoms on the symptom questionnaire scored as absent.

The proportion of participants that achieve symptom resolution at Days 5, 7, 11, and 22 will be summarized in frequency tables and listed.

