# 6.16.2. Additional Exploratory Analyses Not Defined in the Protocol

In addition to the protocol defined endpoints, additional sensitivity analyses may be performed if deemed appropriate. Analyses of hospitalization events will be performed utilizing the safety population.

Additional analyses include:

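### The SAP names two different populations for COVID-19-related deterioration, and membership of one of them can depend on the outcome (minor)

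*SAP*

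**What the plan says.** The SAP assigns this endpoint to a population in two places, and they disagree.

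- SAP 6.1.1, Table PYAB.6.1, gives the purpose of the safety population as: "Used for safety analyses, analyses of COVID-19-related deterioration and hospitalization events".
- SAP 6.16.1.4 defines deterioration as COVID-19-related hospitalization or death from any cause by Days 22, 29, 60 and 85, adds a Day 29 composite that includes emergency room visits, and closes with: "The efficacy population will be utilized to analyze COVID-19-related deterioration".

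The definitions of the two populations differ:

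- Safety (SAP Table PYAB.6.1): "All enrolled participants who received any amount of study intervention".
- Efficacy (SAP Table PYAB.6.1): "All enrolled participants who received study intervention and provided at least 1 postbaseline efficacy measurement".
- Efficacy (Protocol 2.10.3): "All pediatric participants who received study intervention and provided at least one post-baseline measure for the relevant endpoint".

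SAP 6.16.2, which covers analyses not defined in the protocol, adds: "Analyses of hospitalization events will be performed utilizing the safety population". On the symptom questionnaire, SAP 6.16.1.2 states: "This questionnaire is for outpatient participants only".

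**The concern.** Two programmers could each follow the SAP and produce different denominators for the same proportion. Membership of the safety population is settled at dosing. Membership of the efficacy population is settled afterwards, by whether a post-baseline measurement exists, and that can be affected by the very events being counted. Because the SAP does not say what an efficacy measurement is, it is also unclear which children would leave. With few events expected, the handling of one child could decide the reported result.

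**Working it through.** The plan gives no figure for this endpoint, so there is none to reproduce. The check compares the texts and then illustrates the size.

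**1. Is the conflict resolved anywhere?** SAP 6.1.1 has an override clause for cases specified otherwise, but it covers treatment groups and inferential comparisons, not a population's purpose. The conflict between Table PYAB.6.1 and 6.16.1.4 stands.

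**2. Who could leave under the SAP definition?** In the Protocol's Schedule of Activities (2.2.1), symptoms are collected after baseline on Days 2 to 11, 22, 29 and at early discontinuation. Swabs are taken on Days 5, 7, 11, 29 and at early discontinuation. SAP 6.16.1.2 restricts the questionnaire to outpatients. If only symptom and swab data count as efficacy measurements, a treated child who dies or is admitted within about a day of dosing, and has no later symptom or swab record, is outside the efficacy population. The event leaves the numerator and the child leaves the denominator, so the proportion falls.

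**3. Who could leave under the Protocol definition?** The measure must be one for the relevant endpoint. A recorded hospitalization or death can then qualify the child by itself, so children with events stay. Event-free children with no follow-up have no such measure and can leave, so the proportion rises.

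**4. Expected counts.** Inputs: about 50 children aged 0 to 12 years and up to about 20 adolescents (SAP 5.3), hence up to about 70; background hospitalization of 0.1-1.5% (Protocol 2.5). Expected events = n × p; chance of at least one = 1 − (1 − p)^n.

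| n | p | Expected | Chance of at least one |
|---|---|---|---|
| 50 | 0.1% | 0.05 | 4.9% |
| 50 | 1.5% | 0.75 | 53.0% |
| 70 | 0.1% | 0.07 | 6.8% |
| 70 | 1.5% | 1.05 | 65.3% |

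**5. Effect of an exclusion (assumed counts, exact Clopper-Pearson 95% intervals).**

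| Case | Result | 95% CI |
|---|---|---|
| 50 treated, one event, all counted | 1/50 = 2.0% | 0.05% to 10.65% |
| Child with the event excluded | 0/49 = 0% | 0% to 7.25% |
| One event-free child excluded | 1/49 = 2.04% | 0.05% to 10.85% |
| 70 treated, one event, all counted | 1/70 = 1.43% | 0.04% to 7.70% |
| Child with the event excluded | 0/69 = 0% | 0% to 5.21% |

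Losing a child with an event matters far more to the estimate than losing one event-free child.

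**The case against.** The strongest reply is that the bias is speculative and the consequence small. Most of that stands.

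- A reader might infer that the efficacy population biases the proportion toward zero. The documents do not support a fixed direction. Under Protocol 2.10.3 the event record may itself qualify the child, and the Schedule of Activities collects hospitalization events from Day 2 at every contact, accepting hospital records for clinical status.
- Exclusion of a survivor would be rare even under the narrow reading. A discharged child is an outpatient again, with symptom collection up to Day 29 and further swabs. Protocol 2.9.1 has no outpatient-only limit. What remains is mainly death or complete loss very soon after dosing. At the cited death rate of at most 0.02%, 50 × 0.0002 = 0.01 deaths are expected at any time.
- The 0.1-1.5% covers all pediatric hospitalizations, not early ones without later records, so it does not estimate how many children would be excluded.
- A reader might also take a mismatch between the deterioration and hospitalization tables as a fault in itself. It is not: SAP 6.16.2.4 covers hospitalization at any time, possibly for any cause, while 6.16.1.4 requires COVID-19-related stays of at least 24 hours, or death. They can differ with the same denominator. The sentence in 6.16.2 concerns the additional analyses and does not by itself contradict 6.16.1.4.
- No event is hidden. SAP 6.12.5 lists all hospitalization events, and 6.12.4 provides narratives for deaths and serious adverse events.

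The reply does not remove the written conflict or supply the missing definition. The Protocol wording might keep children with events in, but the SAP wording is different, and either reading makes membership depend on what happens after dosing.

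**Conclusion.** The point holds as a minor inconsistency. The SAP assigns one endpoint to two populations, and one of them has an undefined, post-baseline membership rule that can depend on the outcome. The bias could run down (SAP wording) or up (Protocol wording), and few children would be affected.

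The change from 2.0% to 0% is an illustration with an assumed early event, not an estimate. The expected counts assume that the cited background rate applies to this cohort. A reader might infer from them that at most one event can occur, but they are expectations, not bounds: at 1.5% and n = 50, the chance of two or more is 1 − 0.985^50 − 50 × 0.015 × 0.985^49 = 1 − 0.470 − 0.358, about 17%.

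The endpoint is exploratory and descriptive, efficacy is extrapolated from adults (Protocol 2.5), and the primary PK analysis does not use this population.

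**What to change.** Replace the last sentence of SAP 6.16.1.4 with: *The safety population (every participant given any amount of study drug) will be used for COVID-19-related deterioration.* Apply it to the Day 22, 29, 60 and 85 composites and to the Day 29 composite with emergency room visits. This agrees with Table PYAB.6.1 and fixes membership at dosing under either definition of the efficacy population.

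The cost is one sentence, with no new data and no change in conduct. There is a small downside: if only observed events are counted, as SAP 6.16.2.4 does for related proportions, treated children lost early count as event-free, which pulls the proportion down. Report the number without follow-up to each time point beside each proportion, so that readers can judge the effect.

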#### 6.16.1.5. Viral Resistance

If appropriate, the evaluation of viral resistance will be conducted as described in a separate bioanalytical analysis plan.

# 6.16.2. Additional Exploratory Analyses Not Defined in the Protocol

In addition to the protocol defined endpoints, additional sensitivity analyses may be performed if deemed appropriate. Analyses of hospitalization events will be performed utilizing the safety population.

Additional analyses include:

### 6.16.2.1. Time to Hospitalization

Time to Hospitalization is defined (in days) as:

(First study day when hospitalized status is changed to "Yes" – Infusion Date +1)

If a patient has been admitted to the hospital or ICU by completion or early discontinuation of study/study treatment, the patient will be censored at the date of their last visit during the treatment period.

Time to hospitalization will be evaluated during the study treatment period only, summarized with the Kaplan-Meier survival plot and listed.

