2.5. Section 4.2. Scientific Rationale for Study Design

COVID-19 is a severe viral respiratory infection caused by SARS-CoV-2 that affects all age groups (Hoang et al. 2020).

SARS-CoV-2 Incidence in the Pediatric Population

Children of all ages may be infected with SARS-CoV-2. As of April 2022, child COVID-19 cases represented 19.0% of all COVID-19 cases reported, with an overall rate of 17,061 cases per 100,000 children in the US (AAP 2022).

Severity of Disease

While COVID-19–associated hospitalizations and deaths have occurred more frequently in adults (Delahoy et al. 2021), there are still pediatric patients who are infected with SARS-CoV-2 that become hospitalized (0.1-1.5%), and 0.00%-0.02% of all pediatric cases result in death (AAP 2022). There are also concerns about potential later term sequela that may result in pediatric patients from SARS-CoV-2 infections (Hertting et al. 2021), including MIS-C, an uncommon (approximately 2.1 in 100,000 persons <21 years of age [Belay et al. 2021]) but potentially fatal condition that occurs approximately 2 to 6 weeks after infection (CDC 2021).

As in adults, outcomes in pediatric patients of all ages are generally worse in the presence of a number of comorbid conditions, such as

- medical complexity requiring long-term technological support,
- obesity,
- diabetes,

- asthma,
- chronic lung disease,
- sickle cell disease, or
- immunosuppression.

However, in severe disease resulting in hospitalization among pediatric patients, approximately one-third of hospitalizations occur in patients that do not have an underlying medical condition (Wanga et al. 2021; Woodruff et al. 2021).

Unmet Need for Treatment

Currently, there are limited authorized or approved therapies effective for the treatment of the Omicron variant of COVID-19 in non-hospitalized pediatric patients under 12 years of age or 12 to 17 and weighing less than 40 kg body weight, which necessitates the urgent need to have access to experimental therapies.

Extrapolation of Efficacy

Efficacy will be fully extrapolated from adult data. The rationale behind this extrapolation of efficacy from adult efficacy studies to pediatric patients is based on

- FDA guidance documents (FDA 2020; FDA February 2021; FDA December 2021)
- the common initial stages of COVID-19 in (adult and pediatric patients when viral infection and replication occurs)

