# 5.3. Determination of Sample Size

### Sample Size

There is an urgent unmet need among pediatric patients since there are no approved vaccines for the prevention of COVID-19 in pediatric patients <6 months of age and no FDA-approved therapies effective for treatment of the Omicron variant in patients <12 years or outside the existing bebtelovimab EUA criteria. Consequently, this study will include SARS-CoV-2 positive pediatric patients with mild to moderate disease that are 0 (≥38 weeks gestational age and ≥ 3.3 kg) to <12 years of age, or 12 to 17 years of age and weighing <40 kg.

The planned sample size is approximately 50 participants that are 0 ( $\geq$ 38 weeks gestational age and  $\geq$ 3.3 kg) to 12 years of age, with a minimum of 5 participants in each of these age groups

0 to <2

2 to <6 years, and

6 to <12 years

Participants who are 12 to 17 years of age and weighing less than 40 kg can be enrolled into the study until approximately 50 participants that are 0 ( $\geq$ 38 weeks gestational age and  $\geq$  3.3 kg) to 12 years of age are fully enrolled.

Fifty participants would provide adequate study power to target a 95% confidence interval within 60% to 140% of the geometric mean estimates of clearance and volume of distribution (Wang et al. 2012) for bebtelovimab as can be seen in Figure PYAB.5.2.

Participants who are 12 to 17 years (and weighing <40 kg) can be enrolled, up to approximately 20 participants. Enrollment for this group may continue (up to 20 participants) until approximately 50 participants <12 years have been fully enrolled.

[figure not shown]

Figure PYAB.5.2. Estimated study power to target a 95% confidence interval within 60% to 140% of the geometric mean estimates of clearance and volume of distribution.

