### 6. A Priori Statistical Methods

### 6.1. General Considerations

Statistical analysis of this study will be the responsibility of the sponsor or its designee.

All tables, figures, and listings will be created using the clinical trial database (unless otherwise noted), including data during study participation. While not reflected in a table, figure, or listing, any data collected after study participation (e.g., in the Lilly Safety System or collected through queries to the investigator) may be discussed in a clinical study report (CSR) or integrated summary document when deemed relevant.

Not all displays described in this statistical analysis plan (SAP) will necessarily be included in the CSR. Not all displays will necessarily be created as a "static" display. Some may be incorporated into interactive display tools instead of, or in addition to, a static display. Any display described in this SAP and not provided would be available upon request.

Subgroup analyses (by age and weight categories, see Section 5.3) will be performed as appropriate and include descriptive statistics only.

For a binary endpoint collected in a longitudinal fashion, a generalized linear mixed-effect model may be applied assuming missing at random (MAR) if deemed appropriate.

All statistical analyses will be performed using SAS software Version 9.4 (or a higher version), FACTS 6.0 (or a higher version), and/or R 3.6 (or a higher version).

Any analyses of exploratory endpoints or sensitivity analyses will be done only if considered warranted by the team, based upon sufficient sample size.

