# 6.1.3. Study Time Intervals

To calculate the length of any time interval or time period in this study, the following formula will be used:

 $Length\ of\ interval\ (days) = End\ Date - Interval\ Start\ Date + 1$ 

To convert any time length from days to weeks, the following formula will be used:

Length of interval (weeks) = Length of interval (days)/7

Only for the purpose of calculating the length of study period time intervals, the words "prior to" in Table PYAB.6.2 should be understood to mean "the day before" while the words "after" should be understood to mean "the day after." For the purpose of determining whether a date/time lies within an interval, these words are intended to convey whether the start or end of the period is inclusive of the specified date.

Table PYAB.6.2. Definition of Study Period Time Intervals

Study Period	Interval Start Definition	Interval End Definition
Screening: All participants who sign informed consent/assent are considered as entering the Screening Period.	Informed consent/assent date	Prior to the start of Treatment and Assessment Period.
Treatment and Assessment Period: All participants who have treatment initiated are considered as entering the Treatment Period.	At the start of study drug administration date/time.	The minimum of treatment period discontinued date, study discontinuation date, or first Post-Treatment Follow-Up visit date.
Post-Treatment Follow-Up: All participants who had a follow-up visit are considered as entering follow-up period.	After the Treatment and Assessment Period ends.	The maximum of the last study visit date or study disposition date.

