# 6.12.5. Hospitalization, Clinical Events, Clinical Status, and Environmental Risk Factors

The following events (observed at any time point during the study treatment period) will be summarized as described in Sections 6.16.2.1, 6.16.2.2, 6.16.2.3, and Section 6.16.2.4.

proportion of participants hospitalized

duration of hospitalization (DOH; in days)

proportion (percentage) of participants admitted to Intensive Care Unit (ICU), and proportion (percentage) of participants requiring mechanical ventilation (oxygen source = "Intubation/Mechanical Ventilation")

All hospitalization events, procedures of special interest, and environmental risk factors will be listed.

In the event that a participant has an ongoing hospitalization event at the time of study disposition, the hospitalization end date will be imputed to the study disposition date.

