# 6.16.1.3. Time to Symptom Resolution and Sustained Symptom Resolution Time to symptom resolution is defined (in days) as:

(First study day when symptom resolution status is changed to "Yes" - Infusion Date + 1)

If a patient has not experienced symptom resolution by completion or early discontinuation of study/study treatment, the patient will be censored at the date of their last visit during the treatment period. If a patient is hospitalized, the patient will be censored at the date of hospitalization.

Time to symptom resolution will be evaluated during the study treatment period only and will be summarized and listed.

Time to symptom resolution will be presented graphically.

Sustained symptom resolution occurs at the first visit where symptom resolution is observed without reoccurrence at any subsequent visits. Time to sustained symptom resolution in the same manner as described for initial symptom resolution and will be analyzed and summarized in the same way.

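### SAP 6.16.2.1 and 6.16.2.3 censor the patients who were admitted, so under the literal rule neither Kaplan-Meier curve can show an event

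*SAP*

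**What the plan says.** SAP 6.16.2.1 measures time to hospitalization from the infusion date to the first study day on which hospitalized status becomes yes, plus one. SAP 6.16.2.3 does the same for ICU status. Both then give the same censoring sentence: "If a patient has been admitted to the hospital or ICU by completion or early discontinuation of study/study treatment, the patient will be censored". The censoring date is the last visit in the treatment period. Both endpoints are evaluated in the treatment period only, and each gets a Kaplan-Meier plot and a listing.

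The SAP's comparable rule for time to symptom resolution, in 6.16.1.3, points the other way: "If a patient has not experienced symptom resolution by completion or early discontinuation of study/study treatment, the patient will be censored".

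Three other places bear on this:

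- Table PYAB.6.2 ends the treatment period at "The minimum of treatment period discontinued date, study discontinuation date, or first Post-Treatment Follow-Up visit date".
- SAP 6.12.5, in the safety chapter, says hospitalization and ICU events "will be summarized as described in Sections 6.16.2.1, 6.16.2.2, 6.16.2.3, and Section 6.16.2.4".
- SAP 6.16.2 states that "Analyses of hospitalization events will be performed utilizing the safety population".

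On a related point, the Safety row of Table PYAB.6.1 claims the analyses of COVID-19-related deterioration, while SAP 6.16.1.4 gives them to the efficacy population.

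**The concern.** In a time-to-event analysis, patients with the event contribute an event time and patients without it are censored. The two sections do the opposite. They contradict the event definition directly above the rule, and they give no explicit censoring rule for the patients who were never admitted, who will be nearly the whole cohort. Follow-up for those patients is bounded only indirectly, through the treatment-period definition.

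If the rule is programmed as stated, a flat curve at 1.00 could appear beside a listing that shows admissions. The error would run in the favorable direction, in a pediatric safety report.

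**Working it through.** The documents state no event count, power or sample size for these two endpoints, so there is no figure of the plan's to reproduce. The check is first logical, then a matter of scale.

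**1. Can any event survive the rule?**

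- Only admissions inside the treatment period count (6.16.2.1, 6.16.2.3).
- Any such admission has happened by completion or early discontinuation, so it meets the censoring condition.
- Every ICU admission also meets the condition, because the rule covers hospital or ICU.
- The number of events is therefore 0 for any data, and the product-limit estimate stays at 1.00.

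**2. Illustration (assumed data).** Take 50 patients: one admitted on Day 4 and never in ICU, one admitted on Day 9 and in ICU on Day 11, and everyone otherwise last seen on Day 29.

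| Endpoint | Rule as written | Patients without the event censored |
|---|---|---|
| Hospitalization | 0 events, S(29) = 1.00 | 2 events, S(29) = (1 − 1/50)(1 − 1/49) = 0.96 |
| ICU | 0 events, S(29) = 1.00 | 1 event, S(29) = 1 − 1/50 = 0.98 |

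With a single admission in 50, before any censoring, the hospitalization curve should fall to 0.98 and would read 1.00. As plain proportions with exact 95% intervals, that is the difference between 1/50 (0.05% to 10.6%) and 0/50 (0% to 7.1%).

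**3. Does adding the missing negative repair both sections?** In 6.16.2.1, yes. In 6.16.2.3 the rule would censor only patients admitted neither to the hospital nor to the ICU. The patient admitted on Day 4 and never in ICU would have no ICU event and would not meet the censoring condition, so no time is defined. That is 1 of the 50 here.

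**4. How likely is it to show?** Inputs:

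- Background pediatric hospitalization of 0.1% to 1.5% (Protocol addendum 2.5). That it applies to this cohort is an assumption.
- n = 50 (SAP 5.3).
- n = 50 + 20 = 70 if the 12 to 17 year group fills; SAP 5.3 says these patients "can be enrolled, up to approximately 20 participants".

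Expected admissions = n × p. Chance of at least one = 1 − (1 − p)^n.

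| n | p | Expected admissions | P(at least one) | P(none) |
|---|---|---|---|---|
| 50 | 0.1% | 0.05 | 4.9% | 95.1% |
| 50 | 1.5% | 0.75 | 53.0% | 47.0% |
| 70 | 0.1% | 0.07 | 6.8% | 93.2% |
| 70 | 1.5% | 1.05 | 65.3% | 34.7% |

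With no admissions the correct curve is flat too, and the error is invisible. The documents give no ICU rate. If ICU admission implies hospitalization, these chances are upper bounds for the ICU curve under the same assumption.

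**5. Population for deterioration.** The Safety row of Table PYAB.6.1 and SAP 6.16.1.4 name different populations for the same endpoint. The efficacy population is itself defined in two ways: Protocol addendum 2.10.3 ties the post-baseline measure to the endpoint being analyzed, while the SAP accepts any post-baseline efficacy measurement. No numeric effect can be derived. It is probably small, because the Schedule of Activities records hospitalization events at every contact from Day 2.

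**The case against.** The strongest reply is that the text contradicts itself more than it forces a flat curve. The event-time formula above the rule gives every admitted patient an event time, and 6.16.1.3 shows the intended pattern. A competent programmer would probably follow the formula and notice the missing word. This is fair as a forecast. It does not make the stated rule right, and a silent insertion of the word would leave the ICU gap in place.

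Second, the effect on safety reporting is limited. The four summaries named in SAP 6.12.5 are proportions and a duration, not time-to-event quantities. SAP 6.16.2.4 counts admissions as observed without imputation, and 6.12.5 lists all hospitalization events. This stands: the proportions, the listings and the primary PK endpoint do not depend on the censoring rule.

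Third, the analyses may not be run at all: "Any analyses of exploratory endpoints or sensitivity analyses will be done only if considered warranted by the team, based upon sufficient sample size". This stands too, and no stated decision rests on the curves.

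Fourth, the background range describes infected children in general. The event in 6.16.2.1 is any hospitalization, and exclusion criterion 32 allows children in hospital for reasons other than COVID-19, so the range need not bound the rate here. That is why the chances above are given for scale only.

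**Conclusion.** The point holds. In both sections the censoring rule is the reverse of what the event definition requires, and no other text corrects it. Read literally, the result is certain: zero events and survival of 1.00 for any number of admissions, against 0.98 for one admission in 50.

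Whether this would be visible depends on there being an admission. The chance is 5% to 53% at n = 50 and 7% to 65% at n = 70, on the assumption that the protocol's background range carries over.

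The consequence is modest, for the reasons granted above. The correction should still be made, because the rule is wrong as written, the obvious one-word repair is incomplete for ICU, and the change costs almost nothing. The population conflict for deterioration is real, but no numeric effect is claimed for it.

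**What to change.** - **SAP 6.16.2.1:** apply the censoring rule to a patient who *has not been admitted to the hospital*.
- **SAP 6.16.2.3:** apply it to a patient who *has not been admitted to the ICU*, with no mention of the hospital, so that a patient hospitalized but never in ICU is still censored.
- **Both:** keep the stated censoring date, the last visit in the treatment period.
- **Table PYAB.6.1 and SAP 6.16.1.4:** name one population for COVID-19-related deterioration. The safety population is preferable because it keeps every treated participant in the denominator. The two definitions of the efficacy population then no longer matter for this endpoint.

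The cost is two wording corrections and one population reference in the SAP. No new data or visits are needed, and no programming beyond the corrected rule.
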